1.2 RATIONALE FOR STUDY

There is still considerable uncertainty about what oxygen levels premature babies should be targeted to. Although there is clear evidence that targeting babies to a lower oxygen saturation (SpO_2) level is associated with harm, it is not clear whether we have found the optimum oxygen target level which maximises survival benefit.

We believe the question of oxygen targeting is an important one in neonatology, and this proposal would be a safe and reliable way of characterising the actual oxygen levels achieved at a higher SpO_2 target range. We hope the results of this study would inform a larger research study using higher SpO_2 limits and powered to analyse clinical outcomes.

Because very high oxygen levels may cause harm (such as increasing the risk of retinopathy of prematurity - a condition that although treatable can affect vision), it is prudent to increase oxygen target limits by small increments, and for a short amount of time. This is why we are proposing a small increase in SpO₂ target limits from 90-95% to 92-97%, for a short period (6 hours).

Based on previous research it is very unlikely that these slightly higher ranges will be associated with hyperoxia (high levels of oxygen in the blood), but it is also sensible to monitor oxygen levels by more than just SpO₂, as SpO₂ is not the best way of measuring hyperoxia. This is why we are proposing to use transcutaneous oxygen monitoring (TcPO₂) throughout the study, as previous research has demonstrated TcPO₂ is better at detecting hyperoxia than SpO₂.

In order to minimise confounding factors, we propose that infants act as their own controls, being randomised either a higher or standard SpO₂ target limit, and then crossing over to the other SpO₂ target range after 6 hours.

As described above, we feel that the research question is an important one, and our proposal will be able to answer it. We believe this proposal minimises risk to infants. Although previous research has suggested a very high levels of oxygen are associated with increased risk of ROP, there is good evidence to suggest that our proposed slightly higher SpO₂ range will not be associated with hyperoxia, and the use of TcPO₂ is an additional safety measure. We need to balance the risk of ROP with the very real risk that we are missing the opportunity to reduce mortality in premature babies by not using an SpO₂ target range that is high enough to achieve maximum survival advantage.

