2.1.2 Secondary Objectives

To discover the percentage time spent above a TcPO₂ of 80mmHg and below a TcPO₂ of 50mmHg when infants are targeted to an SpO₂ range of 92-97% compared to 90-95%

To discover the variability in SpO₂ (measured by standard deviation) when infants are targeted to an SpO₂ range of 92-97% compared to 90-95%

To discover the variability in TcPO₂ (measured by standard deviation) when infants are targeted to an SpO₂ range of 92-97% compared to 90-95%

In infants who are undergoing PaO₂ measurement as part of their routine care describe the PO₂ values observed in the two target ranges.

To generate a pooled frequency histogram of percentage time at each SpO₂ point between 80 and 100% for infants targeted to an SpO₂ range of 92-97% compared to 90-95%

To generate a pooled frequency histogram of percentage time at a TcPO₂ of below 30mmHg, 30-39.9mmHg, 40-49.9mmHg, 50-59.9mmHg, 60-69.9mmHg, 70-79.9mmHg, and 80mmHg and above for infants targeted to an SpO₂ range of 92-97% compared to 90-95%

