3 STUDY DESIGN

Summary

This study is a single centre randomised crossover study. Infants born at less than 29 weeks gestation, greater than 48 hours of age and receiving supplementary oxygen would be eligible for inclusion. The study is at the Royal Infirmary of Edinburgh. Total study time is 12 hours for each infant (6 hours at the standard 90-95% range used in our unit, and 6 hours at 92-97%). It is a crossover study with infants acting as their own controls.

A complete list of all monitoring that will be carried out is shown below:

1. SpO₂ monitoring
2. TcPO₂ monitoring
3. Heart rate monitoring (used to validate SpO₂ readings as described below)
4. Arterial gas sampling (only if conducted by the direct care team as part of the routine care of the infant will these be recorded. No extra blood samples will be taken as part of the study)

[figure not shown]
Design

Each infant will be monitored simultaneously with an SpO₂ monitor and TcPo₂ monitor, with data recording starting from the time the transcutaneous monitor finishes calibrating. SpO₂ readings will be downloaded directly from the multiparameter patient monitor. SpO₂ will be measured using a Siemens Infinity SC7000 multiparameter monitor (Siemens Medical Systems, Danvers MA). This monitor uses Siemens' Oxisure pulse oximetry technology and Nellcor Oximax (Nellcor Puritan Bennett, CA, USA) saturation probes and incorporates ECG to reduce motion artefact. To reduce the influence of artefact further, data from an infants chest leads (recording heart rate) will also be downloaded. If there is a greater than 10 beats per minute difference between heart rate measured from the pulse oximeter and heart rate measured from the chest leads, SpO₂ for that time point will be disregarded.

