4 STUDY POPULATION

4.1 NUMBER OF PARTICIPANTS

A sample of 20 preterm babies born at the Royal Infirmary of Edinburgh meeting the inclusion criteria will be recruited. Because we are obtaining pilot data to inform the design of future studies we do not have a basis for a power calculation

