8.2 PROPOSED ANALYSES

For each group we will calculate the percentage of readings above an SpO₂ of 97% and below an SpO₂ of 92%. These percentages will then be compared between groups by using a Student's T-test.

The variability of SpO₂ for each group will be expressed by calculating the standard deviation of all the valid SpO₂ data points in each group. Comparison between variability between groups will be performed by Student's T-test.

Pooled SpO₂ data from each infant randomised to the 90-95% SpO₂ group will then be used to generate time at each SpO₂ point for the group as a whole, expressed as a percentage of the total number of valid SpO₂ readings. This process will then be repeated for the 92-97% SpO₂ target range group.

Pooled TcPO₂ data from each infant randomised to the 90-95% SpO₂ group will then be used to generate time within the following TcPO₂ ranges for the group as a whole: below 30mmHg, 30-39.9mmHg, 40-49.9mmHg, 50-59.9mmHg, 60-69.9mmHg, 70-79.9mmHg, and 80mmHg and above. This will be expressed as a percentage of the total number of valid TcPO₂ readings. This process will then be repeated for the 92-97% SpO₂ target range group.

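### Section 8.2 analyses TcPO₂ only as pooled bands, so the threshold objective gets no within-infant comparison with precision and the TcPO₂ SD objective gets no analysis

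*Combined protocol and SAP*

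**What the plan says.** Section 2.1.2 lists three TcPO₂ objectives, each contrasting the 92-97% target with the 90-95% target:

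- thresholds: "To discover the percentage time spent above a TcPO₂ of 80mmHg and below a TcPO₂ of 50mmHg";
- variability: "To discover the variability in TcPO₂ (measured by standard deviation";
- a pooled frequency histogram in seven bands, from below 30 mmHg to 80 mmHg and above.

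Section 8.2 has one paragraph on TcPO₂. It pools the readings of all infants at one target range, finds the time in those seven bands, and repeats this for the other range. On the denominator it says: "This will be expressed as a percentage of the total number of valid TcPO₂ readings". The two Student's t-tests in 8.2, one on percentages and one on variability, are written for SpO₂ only. Section 7 adds only that valid TcPO₂ data will be used in the analysis.

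On design, section 3 says: "It is a crossover study with infants acting as their own controls". On size, section 4.1 says: "A sample of 20 preterm babies born at the Royal Infirmary of Edinburgh meeting the inclusion criteria will be recruited", and adds that "we do not have a basis for a power calculation". Section 1.2 gives the reason for measuring TcPO₂: it "is better at detecting hyperoxia than" SpO₂.

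**The concern.** Two of the three TcPO₂ objectives ask for a comparison between target ranges, but the analysis section describes only one pooled distribution per range. Followed as written, the report would show two percentages above 80 mmHg and two below 50 mmHg. It would give no statement of how far the differences could be due to infant-to-infant variation, and nothing on TcPO₂ variability.

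The crossover was chosen so that each infant is compared with itself, and pooling across infants gives up that advantage. Pooling over readings also lets an infant with more valid data count for more. Unequal amounts are possible: section 3 discards segments with air-bubble spikes and moves the probe every 2 hours, and section 9 allows an infant's study to be discontinued.

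At stake is how well the pilot can describe the change in oxygen tension at the higher target, using the measure that the protocol itself regards as better for detecting hyperoxia.

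**Working it through.** **1. Objectives against analyses**

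| TcPO₂ objective (2.1.2) | What 8.2 provides |
|---|---|
| % time above 80 and below 50 mmHg, compared | Pooled point estimates only: the top band (80 and above), and the sum of the three lowest bands (below 50). No difference with precision, no pairing |
| SD, compared | Nothing |
| Pooled histogram in seven bands | Exactly what is asked |

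There is also a small boundary mismatch: the objective says above 80 mmHg, while the top band includes 80.

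**2. Readings against independent units**

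Inputs: 6 hours per target range, one reading per second and 20 infants (sections 3 and 4.1).

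- Readings per infant and period: 6 × 3,600 = 21,600.
- Readings per target range: 20 × 21,600 = 432,000 at most.
- Independent units: 20 infants, each contributing to both ranges.

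The precision of a between-range difference comes from the 20 within-infant differences. The pooled percentages do not contain that information.

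**3. Effect of weighting by readings (invented example)**

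Suppose one infant spends 50% of valid time at 80 mmHg or above and the other 19 spend 2%. The infant mean is (50 + 19 × 2)/20 = 4.4% and the median is 2%. Let the other 19 each have a fraction f of the first infant's valid readings. The pooled percentage is (50 + 19 × 2 × f)/(1 + 19 × f).

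- f = 1: 88/20 = 4.4%.
- f = 0.5: 69/10.5 = 6.6%.
- f = 0.25: 59.5/5.75 = 10.3%.

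No infant's own percentage changes; only the weights do. The example shows the direction and mechanism. It is not a forecast.

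**4. Precision of a within-infant analysis**

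The plan gives no alpha, power, effect size or SD, so there is no figure of its own to reproduce. Assume that all 20 infants complete and let SD_d be the SD of the within-infant differences:

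95% half-width = t(0.975, 19) × SD_d/√20 = 2.093 × SD_d/4.472 = 0.468 × SD_d.

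SD_d is not in the documents. For assumed values:

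| SD_d (percentage points) | 95% half-width (points) |
|---|---|
| 5 | ±2.3 |
| 10 | ±4.7 |
| 15 | ±7.0 |
| 20 | ±9.4 |

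Allowing for period costs one degree of freedom. With an assumed 10 infants in each order and SD_d taken within order, the factor is 2.101/4.472 = 0.470, so about 0.47 either way.

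**The case against.** The strongest reply is that the TcPO₂ paragraph does what one objective asks. Section 2.1.2 requests a pooled histogram in these bands, and 8.2 delivers it. That stands: the histogram is not an error and need not be re-weighted. The fault is the missing analysis beside it.

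A reader might infer that the stated method cannot answer the threshold objective at all. The documents do not support that, because the bands are cut at 50 and 80 mmHg and give a pooled estimate at each threshold for each range. What is missing is the within-infant contrast and its precision.

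A reader might also infer that the trial would report falsely narrow intervals by treating 432,000 readings as independent. Section 8.2 plans no test, standard error or interval on pooled TcPO₂ readings, so there is no such interval to criticise.

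A third inference is that the pilot must supply the SD of TcPO₂ differences to size the next trial. Section 1.2 says the larger study would be powered on clinical outcomes, and section 8.1 mentions TcPO₂ ranges only as a possibility. The SD is worth reporting, but the documents do not make it a sizing input.

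Nor does the bedside safety role of TcPO₂ depend on this comparison. Alarms, the researcher's presence and adverse event recording (sections 6.1, 9 and 9.2) operate without it.

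Three further points carry some weight. These are secondary objectives in a pilot of 20. Section 3 reports that artefact has not been a material problem in routine use, so the weighting effect may be small. And because data are recorded every second, the comparison could still be computed later; it is unspecified, not lost. These points limit the importance of the gap. They do not supply an analysis for a stated objective.

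**Conclusion.** The point holds in a limited form. Two comparative TcPO₂ objectives are set. One receives only reading-weighted point estimates, without pairing or precision; the other receives nothing, and no other section fills the gap. The plan should be corrected on this, but neither the pooled histogram nor the bedside safety monitoring is called into question.

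The size is modest and cannot be stated in mmHg or percentage points without an outside figure. With 20 completers, a t-based 95% half-width is about 0.47 SD of the within-infant differences. This assumes no drop-out and differences that a t-interval describes adequately. The second assumption may fail for time above 80 mmHg: sections 1.2 and 6.1 regard hyperoxia as very unlikely at the higher target, so many infants may have values at or near zero.

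The lack of stated pairing and of intervals is not confined to TcPO₂. The SpO₂ analyses in 8.2 share it, so copying that paragraph across would not be enough.

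**What to change.** Add a paragraph on TcPO₂ to section 8.2:

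- For each infant and each target period, compute the percentage of valid TcPO₂ time above 80 mmHg, the percentage below 50 mmHg, and the SD of TcPO₂.
- For each of the three, report the within-infant difference (92-97% minus 90-95%) with a 95% confidence interval, allowing for period, together with the SD of the differences.
- State in advance that if time above 80 mmHg is mostly zero, a median difference with a rank-based or bootstrap interval will be used.
- Make the upper boundary the same in 2.1.2 and 8.2 (above 80, or 80 and above).
- Keep the pooled histogram as the descriptive display that 2.1.2 asks for.

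In a pilot of this size the estimates and intervals matter more than tests. The cost is a few lines of protocol text and little analysis time; the readings are already to be collected.

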9 ADVERSE EVENTS

This study uses monitoring equipment that has been used routinely in neonatal units for many years, and therefore the risk of adverse events is small. By targeting babies to higher oxygen saturation levels there is a possibility that they will be subjected to higher oxygen levels than previously recommended for short periods. Previous research and audit of our unit's blood gas machine results suggests that at a SpO₂ target range of 92 to 97% this is very unlikely, and is in fact more likely to keep infants within the previously suggested oxygen tension target range. The risk of hyperoxia in infants is mitigated by the short study period and the use of transcutaneous monitoring which detects hyperoxia better than saturation monitoring.

The researcher will be present throughout the short study period for each infant. If the direct care team feel that the additional monitoring equipment is interfering in any way with routine care of the infant, the study will be discontinued in that infant.

9.1 DEFINITIONS

This study is not a drug study. The following concerns definitions and reporting of adverse events that may arise due to the study intervention (targeting infants briefly to a slightly higher oxygen saturation range).

An **adverse event** (AE) is any untoward medical occurrence in a clinical trial participant which does not necessarily have a causal relationship with the study intervention.

An **adverse reaction** (AR) is any untoward and unintended response to the study intervention.

A **serious adverse event** (SAE), **serious adverse reaction** (SAR). Any AE or AR that:

- results in death of the clinical trial participant;
- is life threatening*
- requires in-patient hospitalisation[^] or prolongation of existing hospitalisation;
- results in persistent or significant disability or incapacity;
- consists of a congenital anomaly or birth defect;
- results in any other significant medical event not meeting the criteria above.

*Life-threatening in the definition of an SAE or SAR refers to an event where the participant was at risk of death at the time of the event. It does not refer to an event which hypothetically might have caused death if it were more severe.

^Any hospitalisation that was planned prior to randomisation will not meet SAE criteria. Any hospitalisation that is planned post randomisation will meet the SAE criteria.

A suspected unexpected serious adverse reaction (SUSAR) is any AR that is classified as serious and is suspected to be caused by the study intervention, that it is not consistent with previous research and hypotheses highlighted in the Study Protocol.

9.2 IDENTIFYING AEs AND SAEs

All AEs and SAEs will be recorded from the time a baby commences the first study period until 1 week after the final participant has completed the study. Adverse incidents may include skin redness following the use of transcutaneous probes or periods of hyperoxia.

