Three recent systematic reviews and meta-analyses using data from the five studies that make up the NeOProM collaboration have all revealed a significant increase in the risk of death associated with targeting infants to the lower SpO_2 range. Saugstad OD, Aune D⁽³⁾ found relative risks (RR; 95% CIs) comparing a low versus a high oxygen saturation target were 1.41 (1.14-1.74) for mortality at discharge or at follow-up. Manja and Lakshminrusimha⁽⁴⁾ found a significant increase in mortality before hospital discharge in infants targeted to the lower SpO_2 range (RR, 1.18 [95% CI, 1.03-1.36]). Askie et al.⁽⁵⁾ found a lower SpO_2 target range significantly increased the incidence of death at 18 to 24 months corrected age (typical RR 1.16, 95% CI 1.03 to 1.31; typical RD 0.03, 95% CI 0.01 to 0.05; 5 trials, 4873 infants).

As described above, the search for the optimum oxygen level to target preterm infants is still ongoing. Although there is very good evidence targeting infants to a lower oxygen level results in harm, it is not clear whether the higher target level used in the NeOProM studies achieves the optimum survival advantage.

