5.2.1 Withdrawal of Study Participants

Parents will be free to withdraw their infant from study at any time without having to give a reason. As the study involves routinely used equipment and is of short duration it is not anticipated that this will happen.

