8 STATISTICS AND DATA ANALYSIS

8.1 SAMPLE SIZE CALCULATION

This is a pilot study to inform a larger study of SpO₂ and possibly TcO₂ ranges.

Recruitment is planned to end when 20 babies have been recruited and randomised. Based on the frequency of delivery of preterm babies in our unit we estimate the study to last 1 year.

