9.4.2 Assessment of Causality

The Investigator will make an assessment of whether the AE/SAE is likely to be related to the study intervention according to the definitions below.

- Unrelated: where an event is not considered to be related to the study intervention.
- Possibly Related: The nature of the event, the underlying medical condition, concomitant medication or temporal relationship make it possible that the AE has a causal relationship to the study intervention.

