9.5 REPORTING OF SAEs/SARs/SUSARs

Once the Investigator becomes aware that an SAE has occurred in a study participant, the information will be reported to the ACCORD Research Governance & QA Office **immediately or within 24 hours**. If the Investigator does not have all information regarding an SAE, they should not wait for this additional information before notifying ACCORD. The SAE report form can be updated when the additional information is received.

The SAE report will provide an assessment of causality and expectedness at the time of the initial report to ACCORD according to Sections 10.4.2, Assessment of Causality and 10.4.3, Assessment of Expectedness.

The SAE form will be transmitted by fax to ACCORD on **[name]** or may be transmitted by hand to the office or submitted via email to [contact]. Only forms in a pdf format will be accepted by ACCORD via email.

Where missing information has not been sent to ACCORD after an initial report, ACCORD will contact the investigator and request the missing information.

All reports faxed to ACCORD and any follow up information will be retained by the Investigator in the Investigator Site File (ISF).

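### Does section 9.2 leave it unclear when adverse event recording stops for each infant?

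*Combined protocol and SAP*

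**What the plan says.** All references are to the combined protocol and SAP.

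- **Recording window (9.2).** Recording starts for each infant with that infant's first study period and runs "until 1 week after the final participant has completed the study". Skin redness from the probe and spells of hyperoxia are given as possible examples.
- **What counts (9.1, 9.4.2).** An adverse event need not be caused by the intervention. It is serious if, among other criteria, it "results in death of the clinical trial participant". On admissions, "Any hospitalisation that is planned post randomisation will meet the SAE criteria". Causality has an unrelated class, "where an event is not considered to be related to the study intervention".
- **Reporting (9.3, 9.5, 9.6).** Onset date is collected for every event. The 24-hour duty to tell the sponsor's office begins "Once the Investigator becomes aware that an SAE has occurred in a study participant", and 9.5 has no end date of its own. The annual report in 9.6 lists serious adverse reactions and SUSARs.
- **Size and length (3, 8.1).** Each infant is studied for 12 hours. Recruitment ends once 20 infants are recruited and randomised, and "we estimate the study to last 1 year".
- **Leaving early (5.2.1, 9).** "Parents will be free to withdraw their infant from study at any time", and the study stops in an infant if the care team finds that the extra monitoring interferes with care. Neither section gives a separate end date for adverse event recording.
- **End of study (12.5).** This is set by the last participant's last visit.
- **Analysis (8.2).** Only SpO₂ and TcPO₂ summaries and comparisons are described. No adverse event analysis is planned.

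**The concern.** A start tied to each infant, a stop tied to the last infant, a 12-hour study and short-lived example events sit oddly together. A reader may suspect that a stop one week after each infant's own completion was meant.

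The choice decides which events belong to the study. Deaths count as serious whatever their cause, so a death 20 weeks after an infant's 12 hours is a reportable event under the wording if that infant entered early. Under a stop per infant it is reportable for nobody. Two infants with the same course could be listed differently only because one enrolled earlier. The sponsor's list of serious events, and any statement about whether deaths occurred, would depend on the reading. Infants who withdraw or are discontinued might also seem to have no end date, because the stop is triggered by completion.

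**Working it through.** The documents give no adverse event rate or exposure figure to reproduce. The check therefore covers the wording, the size of the difference, and what depends on it.

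**1. The wording.** Section 9.2 uses the individual infant for the start and the last infant for the stop. Section 12.5 likewise ends the study by its last participant. The plain sense is one calendar date for all. A stop per infant requires replacing a word, and no section states one.

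**2. Length of recording.** Inputs: 20 infants and 1 year (8.1), 12 hours each (section 3), and 1 week (9.2). Entries evenly spaced from week 0 to week 52 are an assumption. The study time is 12/168 = 0.071 weeks.

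- Common stop: window = 52 + 0.071 + 1 − entry week. The first infant has 53.1 weeks and the last 1.1 weeks. The mean is 27.07, and 20 × 27.07 = 541 infant-weeks.
- Stop per infant: 20 × 1.071 = 21.4 infant-weeks.
- Ratio: 541.4/21.4 = 25.3.

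| Entry pattern (assumed) | Common stop, infant-weeks | Ratio to 21.4 |
|---|---|---|
| Even over 26 weeks | 281 | 13.1 |
| Even over 52 weeks | 541 | 25.3 |
| Even over 78 weeks | 801 | 37.4 |
| 52 weeks, most enter early | 706 | 32.9 |
| 52 weeks, most enter late | 379 | 17.7 |

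For the example of a death at 20 weeks, even entry puts infants 52/19 = 2.74 weeks apart. The windows are then about 53 − 2.74k weeks for k = 0 to 19, and they exceed 20 weeks for k = 0 to 12. That is 13 of 20 infants under the common stop and none under a stop per infant.

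**3. Deaths, as an illustration only.** Section 1.1 quotes, for death at 18 to 24 months with the lower saturation target, "typical RR 1.16, 95% CI 1.03 to 1.31; typical RD 0.03". The risk at the higher target is then RD/(RR − 1) = 0.03/0.16 = 0.19. Study infants have already survived at least 48 hours, so take p from 0.05 to 0.19 (the lower value is assumed). Spread the deaths evenly over 12 or 91 weeks after the study (assumed), and ignore the 12 hours. Expected listed deaths are p × ΣF(w), where F(w) = min(w/12, 1) or min(w/91, 1).

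- Common stop: ΣF = 17.7 (12 weeks) or 540/91 = 5.93 (91 weeks). Expected deaths run from 0.05 × 5.93 = 0.30 to 0.19 × 17.7 = 3.4.
- Stop per infant: ΣF = 20/12 = 1.67 or 20/91 = 0.22. Expected deaths run from 0.05 × 0.22 = 0.01 to 0.19 × 1.67 = 0.32.
- Chance of listing at least one, 1 − Π(1 − pF): 26% to 98% against 1% to 27%.

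These ranges come from assumed risk, timing and complete detection. With p = 0.02, equally an assumption, the common-stop figures fall to 0.12 to 0.35 deaths and 11% to 30%. They are background deaths, not an effect of the intervention.

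**4. What depends on the window.** Both target ranges fall within each infant's 12 hours, and one window serves both. The SpO₂ and TcPO₂ analyses in 8.2 do not use it. Unrelated deaths reach the sponsor's office under 9.5 but fall outside the annual list in 9.6. A list collected to the common date can be cut, using onset dates, to any shorter window. The reverse is not possible.

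**5. Infants who leave early.** Under the wording they share the common date. It is undefined only if the last infant does not complete. Counting from the last infant who did complete would, with entries 2.74 weeks apart, close recording before the last infant had entered. The sensible course is to count from the end of the last infant's participation.

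**The case for a change.** The best case for a change grants that the literal reading is clear and says it is still awkward. Infants are nominally followed for about 1 to 53 weeks according to enrolment order. No method is given for finding events after the 12 hours, so late capture would be uneven. Onset dates help an analyst afterwards but do not tell staff during the study when their duty ends. Recording also runs about a week past the end of study in 12.5, and nothing says whether it continues after parents withdraw an infant. One sentence would deal with all of this.

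Part of this stands. Follow-up is unequal, and the position after withdrawal is not spelt out; a sponsor could usefully confirm both points. The rest is weaker. The wording does tell staff when the duty ends, and in a single-centre study of 20 infants that date is easy to know. Unequal follow-up would matter for an event rate or a comparison, and the plan contains neither. A defined summary window would serve an analysis that is not planned. Asking the sponsor to say which stop applies, with either answer acceptable, is a request for confirmation and does not correct an error.

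**Conclusion.** No change is needed. Section 9.2 sets one common stop date. The difference from a stop per infant is large in recording time: about 541 against 21 infant-weeks with even entry over a year, and 13-fold to 37-fold across the entry patterns tried. It has no effect on any planned result. It changes only how many late, mostly unrelated events reach the sponsor's list, and the wider window is the one that can be narrowed later from onset dates. The remaining gaps, a last infant who does not complete and recording after withdrawal, are small enough for the study team to settle in practice. The infant-week figures assume the entry timing. The death figures also assume risk, timing and full detection, and are too wide to support a conclusion. If the sponsor did intend a stop per infant, the wording is a clerical slip whose result is extra recording, with no bias in the SpO₂ or TcPO₂ findings.
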